Appendix 4 Human Body Drawing for Children Aged 2 to 7 Years Old

Day/ Month/20 (examination) Subject identification number: ___S000___

Affected site	Affected area (%)
Face, neck, and head (excluding scalp)	%
Upper limbs	%
Trunk	%
Lower limbs	%
Total	%

Administration site	Treatment area (%)
Face, neck, and head (excluding scalp)	%
Upper limbs	%
Trunk	%
Lower limbs	%
Total	%

Total amount of administration

___ g

 Appropriate amount of administration per 1%
 ___ g

Signature of the investigator/subinvestigator

Day/ Month/20 ___

Amendment No.: 2 (First amendment after submission of protocol)

Date created: 1 Feb 2019

Purpose: To clarify the prohibited concomitant drugs and therapies and exclusion criteria related to prohibited concomitant drugs and therapies and to provide more appropriate wording.

Background: Amendments were made upon judgment that clarifications on prohibited concomitant medication and more appropriate terminology were necessary.

Amendments to protocol:

- The sentence below was added to **Section 4.1 Prohibited Concomitant Drugs and Therapies**. Also, more details were added to clarify the language regarding steroids in **Table 4.1-1 Prohibited Concomitant Drugs and Therapies**.
The use of drugs on the scalp is not restricted since the IMP will not be applied to the scalp.
- In accordance with the above changes, a sentence related to corticosteroids was added to Exclusion Criteria 14 to 16 to allow for the use of corticosteroids on the scalp, and changes to the wording related to corticosteroids were made.

Exclusion Criteria

Prior to change: Subjects who are unable to stop using topical corticosteroids categorized as very strong or higher potency in the “Guidelines for Management of Atopic Dermatitis”¹ from 21 days prior to the baseline examination until the Week 4 examination.

from 21 days p

After change:
Subjects who are unable to stop using topical corticosteroids for skin (excluding scalp) categorized as very strong or higher potency in the “Guidelines for Management of Atopic Dermatitis¹” from 21 days prior to the baseline examination until the Week 4 examination

- Exclusion Criteria 15

Prior to change:

Subjects who are unable to stop using topical corticosteroids categorized as strong potency in the "Guidelines for Management of Atopic Dermatitis"¹, topical immunomodulators, topical retinoids, topical antihistamine and topical non-steroidal anti-inflammatory drugs from 7 days prior to the baseline examination until the Week 4 examination. Intra-ocular, intra-nasal, and intra-auricular corticosteroids, inhaled corticosteroids, intra-ocular and intra-nasal antihistamines or inhaled antihistamines may be considered if, in the opinion of the investigator or subinvestigator, their use will not impact assessment of the affected area.

After change:

Subjects who are unable to stop using topical corticosteroids for skin (excluding scalp) categorized as strong potency in the "Guidelines for Management of Atopic

Dermatitis¹”, topical corticosteroids other than those for skin, topical immunosuppressants, topical retinoids, topical antihistamine and topical non-steroidal anti-inflammatory drugs (excluding for scalp) from 7 days prior to the baseline examination until the Week 4 examination. Intra-ocular, intra-nasal, intra-auricular, and inhaled corticosteroids and antihistamines may be considered if the investigator or subinvestigator judges that their use will not impact assessment of the affected area.

- Exclusion Criteria 16

Prior to change:

Subjects who are unable to stop using topical corticosteroids categorized as low or medium potency in the “Guidelines for Management of Atopic Dermatitis¹” from 4 days prior to the baseline examination until the Week 4 examination.

After change:

Subjects who are unable to stop using topical corticosteroids for skin (excluding scalp) categorized as low or medium potency in the “Guidelines for Management of Atopic Dermatitis¹” from 4 days prior to the baseline examination until the Week 4 examination.

- The following sentence was added to [Section 3.7.1 Schedule of Assessments](#):
Regarding assessments to be performed by the investigator or subinvestigator, the assessments that a clinical trial associate is able to perform (eg, subject demographics and clinical laboratory tests) may be performed by the clinical trial associate under the supervision of the investigator.
- Other changes were made to correct minor typos and to reflect changes to the template.

In this English translation version, the term “immunomodulators” was changed to “immunosuppressants” to standardize terminology across protocols.

## List of Abbreviations and Definition of Terms

### List of Abbreviations

Abbreviation	Expansion or Definition
AE	Adverse event
BMI	Body mass index
BSA	Body surface area
CRF	Case report form
EASI	Eczema Area and Severity Index
FAS	Full Analysis Set
IGA	Investigator's Global Assessment
IMP	Investigational medicinal product
LOCF	Last Observation Carried Forward
MedDRA	Medical Dictionary for Regulatory Activities
MMRM	Mixed Model Repeated Measures
OC	Observed Cases
POEM	Patient-Oriented Eczema Measure
SS	Safety Set
TEAE	Treatment-emergent adverse event
VRS	Verbal Rating Scale

### List of Definitions of Terms

Term	Definition
Descriptive statistics	Number of subjects, mean, standard deviation, maximum, median, and minimum
Frequency distribution	Number and percentage of subjects

## 1 Introduction

This statistical analysis plan describes in detail the methodology for statistical analysis planned in the protocol for Trial 271-102-00008.

## 2 Trial Objectives

Primary objective: To demonstrate the superiority of 0.3% and 1% OPA-15406 ointment to the vehicle when administered the investigational medicinal product (IMP; 0.3% and 1% OPA-15406 ointment or vehicle) twice daily for 4 weeks in pediatric patients with atopic dermatitis (AD), using success rate in Investigator's Global Assessment (IGA) at Week 4 as the primary endpoint.

Secondary objective: To evaluate the efficacy (secondary endpoint) and safety of 0.3% and 1% OPA-15406 ointment when administered the IMP twice daily for 4 weeks in pediatric patients with AD and to confirm the dose-response relationship.

## 3 Trial Design

### 3.1 Type/Design of Trial

This trial is a multicenter, randomized, double-blind, vehicle-controlled, parallel-group, comparison trial to demonstrate the superiority of 0.3% and 1% OPA-15406 ointment to the vehicle in pediatric AD patients. This trial consists of the 0.3% OPA-15406 group, 1% OPA-15406 group, and the vehicle group. The trial design is shown in Figure 3.1-1.

#### 1) Screening period

After obtaining informed consent from the subject's legal guardian (and, if possible, after obtaining assent from the subject), the investigator or subinvestigator will perform a screening examination. The screening period is defined as the period between the day of screening examination and the day of baseline examination (2 to 30 days).

[figure not shown]
#### 2) Assessment period (treatment period)

The assessment period is defined as the period between the day of baseline examination and the end of Week 4 examination (or the end of withdrawal examination). The subjects who meet the inclusion and exclusion criteria at the baseline examination will be allocated to 0.3% or 1% OPA-15406 ointment or the comparator (vehicle [placebo]). The allocated IMP will be administered to the treatment area from the day of baseline examination twice daily for 4 weeks. After the baseline examination, the examinations will be performed at Weeks 1, 2, and 4.

If a subject discontinues the IMP administration between the day of the baseline examination and the day of the Week 4 examination, a withdrawal examination will be performed for that subject.

### 3) Trial period

The trial period for individual subjects is the period from the day of obtaining the written informed consent from the subject's legal guardian to the day of the Week 4 examination or withdrawal examination. For subjects who missed the Week 4 examination or withdrawal examination, the day of discontinuation will be the day when the investigator or subinvestigator determined that the subject was to be withdrawn from the trial. It does not include the follow-up period for adverse events (AEs).

**Figure 3.1-1****Trial Design**

### 3.2 Methods of Administration

#### 3.2.1 Dose, Regimen, and Treatment Period

The 0.3% or 1% formulation or the vehicle of OPA-15406 ointment will be administered twice daily (approximately 12 hours apart between morning and night administration) for 4 weeks. The amount of IMP (g) per dose is 10 g/m^2 BSA and calculated as follows.

- 1) The subject's BSA (m^2) will be calculated based on height and body weight at the screening examination, using the following equation.

$$\text{BSA (m}^2\text{)} = \sqrt{\frac{\text{Ht (cm)} \times \text{Wt (kg)}}{3600}}$$

BSA = body surface area; Ht = height; Wt: body weight (Mosteller 1987)

- 2) The treatment area will be specified.
- 3) The amount of IMP (g) per dose will be calculated as  
“subject's BSA (m^2)” × “treatment area (%)” × “10 g/m^2.”
- 4) Example: In case of a BSA of 0.7m^2 and an affected BSA of 32%:  
 $0.7 \text{ m}^2 \times 0.32 \times 10 \text{ g/m}^2 = 2.24\text{g}$

#### 3.2.2 Treatment Area

The treatment area with the IMP is defined as follows.

- The treatment area selected at the baseline examination will be the affected area determined at the baseline examination.
- After the baseline examination, when the affected area has expanded or a new affected area is detected, the expanded or newly affected area will also be included in the treatment area.
- Even when the affected area is relieved, the IMP administration should be continued there as the treatment area.

The investigator or subinvestigator will instruct the subject's legal guardian (if possible, the subject) regarding the method of administration by specifying the treatment area (%) and the total amount of administration (g) for each treatment area using the human body drawing, and will give the human body drawing (copy) to the subject or subject's legal guardian. The investigator or subinvestigator will record the treatment area (%) of the 4 body regions (face, neck, and head [excluding scalp]; upper limbs; trunk; and lower limbs) in the source document and case report form (CRF).

### **3.3 Trial Population**

The target population of this trial is pediatric AD patients with an IGA score of 2 or 3. Subjects will be included in the trial to reach the target number of 240 subjects for IMP administration (the target inclusion ratio of “2 to 6 years old” to “7 to 14 years old” of age is 1:1). Any withdrawal will not be supplemented.

### **3.4 Trial Visit Window**

The start date of IMP administration is defined as baseline (Day 1) to count the number of days after starting IMP administration. Unscheduled visit data and withdrawal visit data as well as scheduled visit data will be included to determine timepoints for analysis. For efficacy endpoints, data up to 3 days after the end of IMP administration (final day of IMP administration + 3 days) will be included in the analysis. For safety endpoints, all data from the first IMP administration will be included in the analysis. Timepoints for analysis and acceptable windows are shown in Table 3.4-1. If there are multiple data points within an acceptable window, the last one in the window will be used. The Last Visit data for efficacy endpoints will be from the last visit during the period from the day after the first day of IMP administration (Day 2) through the third day after the last IMP administration (including unscheduled and withdrawal visit data), and those for safety endpoints will be from the last visit available from all data after the first day of IMP administration.

The baseline data for analysis will be from the visit closest and prior to the first day of IMP administration.

For the Verbal Rating Scale (VRS), the patient diary will be used as the source of data for the period from the start date of IMP administration (Day 1) through Day 8. After Week 1, CRF Visit data (including unscheduled and withdrawal visit data) excluding patient diary data will be used to specify the timepoints for analysis according to Table 3.4-1. If there are multiple data points within an acceptable window, the last one in the window will be used.

Table 3.4-1 Trial Day and Visit Windows				
Timepoint	Target Day	Interval (days after starting administration)		
Baseline	1	—	to	1
1 day after start of IMP administration (VRS alone)	2	—	to	—
2 days after start of IMP administration (VRS alone)	3	—	to	—
3 days after start of IMP administration (VRS alone)	4	—	to	—
4 days after start of IMP administration (VRS alone)	5	—	to	—
5 days after start of IMP administration (VRS alone)	6	—	to	—
6 days after start of IMP administration (VRS alone)	7	—	to	—
7 days after start of IMP administration (VRS alone)	8	—	to	—
8 days after start of IMP administration (VRS alone)	9	—	to	—
Week 1	8	2	to	10
Week 2	15	11	to	21
Week 4	29	22	to	32

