- Pregnancies are also defined as IREs. Although normal pregnancy is not an AE, it will mandate IMP discontinuation and must be reported on an IRE form to the sponsor. Pregnancy will only be documented on the AE section of CRF if there is an abnormality or complication. Pregnancies of the subjects or their partners will be included in the above.

Clinical Laboratory Test Value Changes: It is the investigator’s responsibility to review the results of all laboratory tests as they become available. This review will be documented by the investigator’s dated signature on the laboratory report. For each abnormal laboratory test result, the investigator needs to ascertain if this is an abnormal (ie, clinically significant) change from baseline for that individual subject. This determination, however, does not necessarily need to be made the first time an abnormal value is observed. The investigator may repeat the laboratory test or request additional tests to verify the results of the original laboratory tests. If this laboratory value is considered medically relevant by the investigator (subject is symptomatic, requiring

corrective treatment or further evaluation), or if the laboratory value leads to discontinuation, and/or fulfills a seriousness criterion, this is considered an AE.

Severity: Adverse events will be graded on a 3-point scale.

1 = **Mild:** Discomfort noticed, but no disruption to daily activity.

2 = **Moderate:** Discomfort sufficient to reduce or affect normal daily activity.

3 = **Severe:** Inability to work or perform normal daily activity.

Skin and subcutaneous tissue disorders will be graded according to the Common Terminology Criteria for Adverse Events v4.0 Japan Clinical Oncology Group edition.

IMP Causality: Assessment of causal relationship of an AE to the use of the IMP is judged according to the following criteria:

Related: There is a reasonable possibility of a temporal and causal relationship between the IMP and the AE.

Not Related: There is no temporal or causal relationship between the IMP and the AE.

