### **9.3 Clinical Laboratory Tests**

For each parameter (except qualitative urinalysis), the descriptive statistics will be calculated for measured values and changes from the baseline at each timepoint by treatment group. For qualitative urinalysis values of clinical laboratory tests, a shift table at each timepoint against the baseline will be created for each treatment group. For clinical laboratory tests except qualitative urinalysis, a shift table for values before and after administration categorized as normal, high, or low relative to the reference value will be created for each treatment group.

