## **9.7 Liver Function Tests**

The number and percentage of subjects with abnormal changes in liver function (Appendix 2) will be calculated by treatment group. Also, a list of abnormal changes in liver function will be created. For clinically abnormal changes, all data after starting administration, except for baseline or missing timepoints, will be included in the evaluation.

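### The last-in-window rule in SAP 3.4 can let an off-treatment repeat blood test displace the abnormal Week 4 or withdrawal result in the SAP 9.3 laboratory tables

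*SAP*

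**What the plan says.** SAP 3.4 treats the two kinds of endpoint differently. For efficacy, "data up to 3 days after the end of IMP administration (final day of IMP administration + 3 days) will be included". For safety there is no such limit: "For safety endpoints, all data from the first IMP administration will be included in the analysis". The same section says of visit types that "Unscheduled visit data and withdrawal visit data as well as scheduled visit data will be included to determine timepoints for analysis", and of competing values that "If there are multiple data points within an acceptable window, the last one in the window will be used". It also defines a safety Last Visit value as the last one available after the first dosing day, again without a limit.

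Protocol 5.1 foresees repeats of abnormal laboratory results: "The investigator may repeat the laboratory test or request additional tests to verify the results of the original laboratory tests".

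SAP 9.3 plans descriptive statistics at each timepoint (CT-10.1.1, CT-10.1.2), a urinalysis shift table at each timepoint (CT-10.2.3) and, for chemistry and haematology (CT-10.2.1, CT-10.2.2), "a shift table for values before and after administration categorized as normal, high, or low relative to the reference value will be created". It does not say which value to use when there are several, and it names no timepoint for the normal/high/low table. SAP 9.7, by contrast, states for liver function: "For clinically abnormal changes, all data after starting administration, except for baseline or missing timepoints, will be included in the evaluation". SAP 9.4 has the same rule for vital signs.

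**The concern.** The only scheduled post-dose laboratory sample is at the Week 4 or withdrawal examination (Protocol Table 3.7-1 and 3.7.6.2). The ointment is collected at that same examination (Protocol 3.7.1.10). A repeat prompted by the result is therefore normally taken off treatment, and it is taken because the first value was abnormal. If the later value is the one tabulated, the replacement is selective: abnormal on-treatment values can be overwritten, while normal ones have no repeat to overwrite them.

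SAP 14 also drops the count, planned in Protocol 7.6.2, of subjects in the potentially clinically significant range. Apart from the Hy's Law combination, CT-10.2 is then the only planned by-arm tabulation of laboratory values outside the reference range. An abnormality that resolves after stopping could appear there as normal.

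**Working it through.** The plan gives no figure to reproduce here. The check is how often the selection rule can act.

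**Inputs from the documents**

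- Windows (SAP Table 3.4-1): Week 1 is Day 2 to 10, Week 2 is Day 11 to 21, Week 4 is Day 22 to 32 with target Day 29.
- Week 4 examination tolerance (Protocol Table 3.7-1): ±3 days, so permitted days are 29 − 3 = 26 to 29 + 3 = 32, which is 7 days.
- Withdrawal days considered: Day 2 to Day 28, which is 27 days.

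**Assumption.** The documents give no repeat interval, so I use lags of 3, 5 and 7 days.

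**Rule.** A first sample on day d and a repeat on day d + lag compete at one timepoint if both lie in the same window. SAP 3.4 then keeps the repeat.

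**Week 4 examination.** The condition is d + lag ≤ 32. The room left is 32 − d: 6 days after a Day 26 visit, 3 after Day 29, none after Day 32.

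- Lag 3: d ≤ 29, so Days 26 to 29, 4 of 7.
- Lag 5: d ≤ 27, so Days 26 and 27, 2 of 7.
- Lag 7: d ≤ 25, so 0 of 7.

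**Withdrawal on Days 2 to 28.** The condition is d + lag ≤ 10, 21 or 32, according to the window of d.

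| Lag | Week 1 window | Week 2 window | Week 4 window | Total |
|---|---|---|---|---|
| 3 days | Days 2–7: 6 | Days 11–18: 8 | Days 22–28: 7 | 21 of 27 |
| 5 days | Days 2–5: 4 | Days 11–16: 6 | Days 22–27: 6 | 16 of 27 |
| 7 days | Days 2–3: 2 | Days 11–14: 4 | Days 22–25: 4 | 10 of 27 |

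These are counts of calendar days, not probabilities, because the distribution of visit days is not known.

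A repeat that crosses into a later window leaves the withdrawal value in place at its own timepoint and puts an off-treatment value at the next one. At a 7-day lag this applies to 14 of the 27 withdrawal days.

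**Last Visit.** This rule has no window. If a table is built from it, a repeat in the data at any lag displaces the earlier value. SAP 9.3 does not say whether the normal/high/low shift table is built this way, and its before-and-after wording leaves that open.

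**Where the rule does not reach.** SAP 9.7 and 9.4 evaluate all data after the start of administration, so a later normal value cannot remove a potential Hy's Law case or a vital-sign abnormality.

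**The case against.** The strongest reply is that the effect is narrow and perhaps rare. After a Week 4 visit on its target day only 3 days of window remain, and some of that goes on central-laboratory turnaround, which is not stated. This stands: a reader might infer from SAP 3.4 that a repeat always replaces the abnormal result, and the window arithmetic shows that it does not.

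It is also unsettled whether such repeats reach the analysis data. The individual trial period ends at the Week 4 or withdrawal examination (Protocol 3.1). The stated trigger for an unscheduled visit is marked enlargement of the affected area (Protocol 3.7.1.11). Follow-up of non-serious events after trial completion goes to medical records (Protocol 5.8.1). On the other side, laboratory tests may be done as necessary at unscheduled visits, and the central laboratory sends results to the sponsor electronically (Protocol 3.7.6.2). The documents do not decide the point.

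A reader might conclude that CT-10.2 is the only by-arm record of laboratory abnormality. It is not. Under Protocol 5.1 a medically relevant value is an adverse event, SAP 9.2 counts TEAEs by arm, and a normal repeat does not delete a reported event. LAB-1 to LAB-3 also list individual results. None of these gives the by-arm comparison against the reference range that CT-10.2 is meant to give.

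A reader might also blame the missing end-of-treatment cut-off. Including all safety data is reasonable and is what protects SAP 9.4 and 9.7. The weakness is choosing the last value.

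Finally, SAP 9.4 and 9.7 count subjects who meet criteria and do not build worst-value shift tables. They supply a principle to extend rather than an exact precedent. Protocol 7.6.2 requires the urinalysis shift table at each timepoint, so that table should keep its form.

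**Conclusion.** The point holds as a conditional one. Applied to SAP 9.3, the last-in-window rule and the open-ended Last Visit rule can let an off-treatment verification repeat displace the single scheduled post-dose result. At a timepoint this needs the repeat to be in the analysis data and in the same window: 4, 2 and 0 of 7 Week 4 visit days, and 21, 16 and 10 of 27 withdrawal days, at assumed lags of 3, 5 and 7 days. The number of repeats is not given, so the number of children affected cannot be estimated.

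The documents do not support a claim that the paediatric safety comparison is materially biased. One can construct a large effect by placing the upper limit at 1.96 SD, letting the drug raise an analyte by 1 SD with full reversal off treatment, and repeating every high value in window. Expected highs on active are then about 13.5 of 80, and 85–91% turn normal on repeat for correlations of 0.9 to 0.5, leaving 13.5 × 0.09 = 1.2 to 13.5 × 0.15 = 2.0. That is an assumed worst case. None of these inputs except the 80 per arm is in the documents, the window arithmetic rules out in-window repeats at many lags, and Protocol 1.2.9 reports no marked laboratory difference among the groups in the paediatric phase 2 trial.

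What remains is a stated rule that can give a wrong by-arm display in descriptive tables, and it is cheap to correct.

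**What to change.** Keep all safety data, with no new cut-off. Add two rules to SAP 9.3:

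1. For the normal/high/low shift tables (CT-10.2.1, CT-10.2.2), classify each child by the highest and by the lowest post-dose value, using all scheduled, withdrawal, unscheduled and repeat samples. This extends the all-data principle of SAP 9.4 and 9.7.
2. For the by-timepoint tables (CT-10.1.1, CT-10.1.2 and CT-10.2.3), use the scheduled or withdrawal sample in preference to a later verification repeat in the same window. Apply the same preference to any laboratory summary built on Last Visit.

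The cost is SAP wording and a small programming change, with no new data and no effect on the efficacy analyses. The downside is that slightly more chance abnormalities will be counted in every arm.

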3.7.1.11 Unscheduled Visits

The investigator or subinvestigator will instruct the subjects to visit the trial site if the area of affected BSA markedly enlarges. The investigator or subinvestigator will perform the following examinations, observations and evaluations, and record the results in the source document and CRF.

- Affected BSA
- AEs
- Concomitant medications and therapies

The following examinations will be conducted as necessary:

- Physical examinations
- Vital signs and body weight
- Clinical laboratory values
- Pregnancy test (only for female children aged 7 - 14 years old)
- IGA
- EASI
- VRS for pruritus (only for subjects aged 7 - 14 years old)

- POEM
- Treatment area
- Photograph of the target site

The investigator or subinvestigator will determine the treatment area (%) and enter it in the IWRS. Also, the investigator or subinvestigator will confirm the subject's allocation status on the IWRS screen and, if necessary, prescribe additional IMP. When the IMP is additionally prescribed, the weight of dispensed IMP will be measured.

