### 8.1.1 Primary Efficacy Analysis

The efficacy of the 0.3% and 1% OPA-15406 groups will be demonstrated compared to the vehicle group based on the primary endpoint, the success rate in IGA at Week 4. Overall type I errors will be controlled using a closed testing procedure. First, the 1% OPA-15406 treatment group and the vehicle group will be compared. If significant at the two-sided significance level of 5%, the 0.3% OPA-15406 treatment group and the vehicle group will then be compared at the two-sided significance level of 5%. The Cochran-Mantel-Haenszel test will be conducted for comparison using the baseline IGA (2 or 3) and age (“2 to 6 years” or “7 to 14 years”) as a stratification factor. The difference in the success rate in IGA and its two-sided 95% confidence interval (common risk difference adjusted by Mantel Haenszel method and its two-sided 95% confidence interval) between the vehicle group and 0.3% or the 1% OPA-15406 group will be determined. Also, the two-sided 95% confidence interval of the success rate in IGA in each treatment group (based on Clopper-Pearson method) will be calculated. In addition, the success rate in IGA in each treatment group at Week 4 and its two-sided 95% confidence interval will be plotted and the dose-response relationship will be graphically assessed.

The SAS code for the Cochran-Mantel-Haenszel test and to determine the difference in the success rate and two-sided 95% confidence interval is as follows:

```
proc freq ;
  tables Agegroup*BaselineIGA*Treatment*Response / riskdiff(common) cmh ;
run;
```

A supplementary analysis will be performed using data which includes missing data imputed by Last Observation Carried Forward (LOCF) and Observed Cases (OC) data which does not include the imputed missing data in the same manner.

Data at Weeks 1 and 2 will also be analyzed in the same manner as the primary endpoint at Week 4.

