### **8.2.2 Change From Baseline Through Week 4 in the IGA Score**

Based on the OC data set, change from baseline (Week 1, Week 2, and Week 4) will be analyzed using a mixed-model repeated measure (MMRM) with treatment (0.3% OPA-15406 or 1% OPA-15406 and vehicle), timepoint, interaction between the treatment and timepoint as factors and baseline values as covariates. An unstructured error covariance matrix will be used and Kenward-Roger method will be used to calculate the degree of freedom. If the MMRM procedure fails to converge under unstructured covariance structure, the following structure will be used in the order of 1) heterogeneous toeplitz, 2) heterogeneous autoregressive of order 1, and 3) heterogeneous compound symmetry, and the first error covariance structure converging will be used. The MMRM analysis with the structured error covariance matrix will use a sandwich estimator. The least square mean will be calculated by treatment group and timepoint.

The SAS code for MMRM analysis is as follows:

```
proc mixed method = reml ;  
  class Treatment Visit Subject ;  
  model Change = Treatment Visit Treatment*Visit Baseline / s ddfm = kr ;  
  repeated Visit / type = un sub = Subject ;  
  lsmeans Treatment*Visit / pdiff cl alpha = 0.05 ;  
run;
```

“Baseline” is baseline IGA data. “Visit” includes data at Weeks 1, 2, and 4.

The SAS code used in the case of convergence failure is as follows: (Specify *type* = *TOEPL* for heterogeneous toeplitz, *type* = *ARH(1)* for heterogeneous autoregressive of order 1, and *type* = *CSH* for heterogeneous compound symmetry.)

```
proc mixed method = reml empirical ;  
  class Treatment Visit Subject ;  
  model Change = Treatment Visit Treatment*Visit Baseline / s ;  
  repeated Visit / type = TOEPL sub = Subject ;  
  lsmeans Treatment*Visit / pdiff cl alpha = 0.05 ;  
run;
```

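### SAP 3.4's last-in-window rule lets an unscheduled visit prompted by worsening replace an on-time Week 1 or Week 2 value (minor; Week 4 endpoints are not overwritten when that examination takes place)

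*SAP*

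**What the plan says.** On which records count toward a timepoint, SAP 3.4 states: "Unscheduled visit data and withdrawal visit data as well as scheduled visit data will be included to determine timepoints for analysis". On ties it states: "If there are multiple data points within an acceptable window, the last one in the window will be used". It gives no priority to the scheduled examination or to closeness to the target day. Table 3.4-1 sets the windows at Days 2-10 for Week 1 (target Day 8), Days 11-21 for Week 2 (target Day 15) and Days 22-32 for Week 4 (target Day 29).

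Protocol 3.7.1.11 gives the trigger for an unscheduled visit: "The investigator or subinvestigator will instruct the subjects to visit the trial site if the area of affected BSA markedly enlarges". Affected BSA, adverse events and concomitant treatment are then recorded in every case. For the rest, including IGA, EASI, VRS and POEM, the protocol says: "The following examinations will be conducted as necessary". Protocol Table 3.7-1 agrees: in the unscheduled-visit column the as-necessary footnote is attached to those four scales and not to affected BSA.

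Weeks 1 and 2 are analysed inferentially. For the responder analysis, SAP 8.1.1 states: "Data at Weeks 1 and 2 will also be analyzed in the same manner as the primary endpoint at Week 4". In the MMRM of SAP 8.2.2, the visit factor "includes data at Weeks 1, 2, and 4". SAP 8.2.2 also specifies ANCOVA differences with confidence intervals and p values at each of these weeks, and SAP 8.2.8 applies the same models to affected BSA.

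**The concern.** The unscheduled visit is triggered by the outcome. A child whose eczema spreads after the on-time examination is measured again, and the later, worse value stands for that week. A child who is stable or improving has no such second look and keeps the scheduled-day value. The later value is a true one, but it is collected selectively, so the arm mean for the named week moves toward worsening in proportion to how often such visits occur. If vehicle children flare more, the early treatment contrast is widened. Blinding does not prevent this, because the difference in visit frequency would come from the treatment effect itself.

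There is also a coherence problem. Affected BSA is always recorded at these visits and the other scales only sometimes, so a child's Week 2 affected BSA and Week 2 IGA may come from different days.

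**Working it through.** **1. Plan figure.** Neither document gives an unscheduled-visit rate or an expected worsening at such visits, so there is no figure to reproduce. The sample size does not depend on this rule.

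**2. Room for an overwrite.** The windows are from SAP Table 3.4-1 and the visit tolerances from Protocol Table 3.7-1 (±2 days at Week 1, ±3 days at Weeks 2 and 4).

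| Timepoint | Window | Visit due (tolerance) | Window days left after the visit |
|---|---|---|---|
| Week 1 | Days 2-10 | Day 8 (6-10) | 10 − 8 = 2 (range 0-4) |
| Week 2 | Days 11-21 | Day 15 (12-18) | 21 − 15 = 6 (range 3-9) |
| Week 4 | Days 22-32 | Day 29 (26-32) | 32 − 29 = 3 (range 0-6), but not usable |

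The Week 4 days are not usable because the subject's trial period ends at that examination (Protocol 3.1, SAP 3.1). An unscheduled visit earlier in any window is itself superseded by the scheduled one.

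**3. Example.** A child is examined on time on Day 15 and attends with spreading eczema on Day 20. Both days lie in Days 11-21. Week 2 affected BSA becomes the Day 20 value. Week 2 IGA, EASI, POEM and VRS become Day 20 values only if scored that day; otherwise they stay at Day 15.

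**4. Formula.** Let f be the share of an arm with an unscheduled visit after the scheduled one in the same window, d the worsening at that visit, and q the chance that the scale is scored there (q = 1 for affected BSA).

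Shift in the arm contrast = (f_vehicle − f_active) × d × q

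With equal f the shift is zero.

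**5. Purely assumed rates for affected BSA.** Take f_vehicle = 5-15%, f_active = 1-4% and d = 10 BSA points.

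- Smallest: (0.05 − 0.04) × 10 = 0.1 points
- Largest: (0.15 − 0.01) × 10 = 1.4 points

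Pairing low with low and high with high gives only 0.4 to 1.1, which hides the near-zero case.

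**6. Rates anchored on phase 2.** In the pediatric phase 2 trial (Protocol 1.2.9), discontinuation for dermatitis atopic was 16.7% on vehicle, 4.2% on 0.3% and 4.0% on 1%. Spread evenly over 28 days (an assumption), with d = 10:

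- Week 2, 6 days: 16.7% × 6/28 = 3.6%; 4.2% × 6/28 = 0.9%; shift (0.036 − 0.009) × 10 = 0.27 points
- Week 1, 2 days: 16.7% × 2/28 = 1.2%; 4.2% × 2/28 = 0.3%; shift (0.012 − 0.003) × 10 = 0.09 points

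**7. IGA.** Assume d = 1 grade and q = 0.25-0.5. The differences in step 5 give 0.01 × 0.25 = 0.0025 to 0.14 × 0.5 = 0.07 grade. The Week 2 difference in step 6 gives 0.027 × 0.25 = 0.007 to 0.027 × 0.5 = 0.013 grade.

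**The case against.** The strongest reply is that nothing decisive is touched. The primary endpoint and every listed visit-based secondary endpoint are at Week 4. Early VRS uses the diary through Day 8. The closed test covers only Week 4 IGA success. This stands, and it is why the point is minor.

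The second reply is that the rule is prespecified, applied identically in all arms, and records a real on-treatment state. That is true, but identical application does not make the estimate neutral when the extra measurement is triggered by worsening.

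The third reply is that the size is guesswork. This also stands. The phase 2 figures count discontinuations over four weeks, not unscheduled visits in a few window days. Children who discontinue have a withdrawal examination instead. The counts are 4, 1 and 1 children; for 4/24 against 1/25, Fisher's two-sided p is about 0.19. The 10-point worsening has no source in the documents.

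The fourth reply concerns the remedy. A blanket preference for scheduled values would also displace withdrawal examinations. A child seen on Day 15 who worsens and withdraws on Day 20 would then enter the observed-case MMRM with only the pre-flare score. This is right, and the fix has to be limited accordingly.

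**Conclusion.** The rule allows a selectively worse value to replace an on-time Week 1 or Week 2 value, and nothing else in the protocol or SAP prevents it. The outputs exposed are supportive: the Week 1 and Week 2 responder comparisons, the MMRM and ANCOVA contrasts, and the by-visit figures. Affected BSA is the most exposed scale. The tilt favours active only if flare visits are commoner on vehicle. Phase 2 hints at that direction but does not establish it.

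The size is unknown. On the stated assumptions it is 0.1 to 1.4 BSA points, and about 0.3 points at Week 2 with the phase 2 rates prorated. Severity is minor.

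Three stronger readings are tempting, and the documents do not support them:

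- **The primary result is biased.** A completed Week 4 examination ends the subject's trial period, so no later visit can replace it. The rule reaches Week 4 only when that examination is missed, or indirectly through LOCF and the MMRM in children without Week 4 data.
- **Affected BSA is always overwritten.** It is always recorded at an unscheduled visit, but it replaces the scheduled value only when that visit comes later in the same window.
- **Phase 2 fixes the magnitude.** It counts a different event, over a longer period, in very few children.

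**What to change.** Add to SAP 3.4, for the efficacy by-visit analyses:

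> If a window contains the scheduled examination for that week, its value is used in preference to any unscheduled-visit value in that window; an unscheduled value is used only when the scheduled value is missing. The same source visit is used for IGA, EASI, POEM, visit VRS and affected BSA where available. Withdrawal-examination data continue to be handled under the existing rule, and the Last Visit and LOCF derivations continue to use all data.

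The last sentence keeps the final observation before dropout in the models. It is also worth stating because the SAP does not say whether LOCF is built from windowed values or from all visits. One residual is accepted: a withdrawal examination prompted by worsening can still replace an on-time value in the same window.

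The cost is this short addition and one programming rule before unblinding. Sample size, visits and procedures do not change, and the overwrite by unscheduled visits at Weeks 1 and 2 falls to zero. The downside is that flare values recorded after the scheduled examination leave the Week 1 and Week 2 summaries. They remain available to Last Visit and LOCF and stay in the listings.
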